10.11.6.2.3. Blinding of the Sponsor for Substudy A

To facilitate rapid review of data in real time, sponsor staff will be unblinded to study intervention allocation for the participants throughout Substudy A.

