10.11.9.4. Interim Analyses for Substudy A

No formal interim analysis will be conducted for this study phase. As the sponsor is unblinded with respect to participants' study intervention assignments (except for staff routinely interacting with sites), the sponsor may conduct unblinded reviews of the data during the course of the study for the purpose of safety assessment, facilitating dose-escalation decisions and/or supporting clinical development.

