10.12.6.2.3. Blinding of the Sponsor for Substudy B

To facilitate rapid review of data in real time, and to allow an assessment of safety data by study intervention group, sponsor staff will be unblinded to study intervention allocation for the participants enrolled during Substudy B.

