10.12.9.5. Analysis Timing for Substudy B

Analyses (immunogenicity or safety) may be performed at any time (eg, safety data through approximately 1 week after vaccination) for all participants.

Complete safety and immunogenicity analysis will be performed at the end of this substudy.

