4. ANALYSIS SETS (POPULATIONS FOR ANALYSIS)

Data for all participants will be assessed to determine if participants meet the criteria for inclusion in each analysis population prior to unblinding and releasing the database, and classifications will be documented per standard operating procedures.

Population	Description
Screened	All participants who sign the ICD.
Randomized	All participants who are assigned a randomization number in
	the IWR system.
Evaluable immunogenicity	All participants who are eligible, receive the study
	intervention to which they were randomized, have blood
	drawn for assay testing within the specified time frame
	(26-35 days after vaccination), have at least 1 valid and
	determinate assay result at the 4-week postvaccination visit,
	and have no major protocol violations.

Population	Description
mITT	All randomized participants who receive the study
	intervention and have at least 1 valid and determinate assay
	result after vaccination.
Safety	All participants who receive the study intervention.

Major protocol deviations will be determined by clinical review. A major protocol deviation is a protocol deviation that, in the opinion of the sponsor's study medical monitor, would materially affect assessment of immunogenicity or efficacy, eg, participant receipt of a prohibited vaccine or medication/treatment that might affect immune response or a medication error with suspected decrease in potency of the vaccine. The sponsor's medical monitor will identify those participants with protocol deviations before any analysis is carried out.

The APE field will be included in the PIPD form from the CORD system and is used to help identify protocol deviations that may exclude participants from a particular population. For each reporting event, the most current endorsed version of the PIPD list must be used to generate the protocol deviation data set for analysis and reporting.

The APE flags for this study are as follows:

YES-POP1 (participants excluded from the safety population)
YES-POP2 (participants excluded from the evaluable immunogenicity population)
YES-POP4 (participants identified as having multiple enrollments at different sites)

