2.3. Study Design

This is a Phase 1/2 substudy to describe the safety, tolerability, and immunogenicity of IRV (qIRV, tIRV, or bIRV) when administered in combination with bivalent BNT162b2 (original/Omi BA.4/BA.5). Bivalent BNT162b2 (original/Omi BA.4/BA.5) will be used during the substudy, as detailed in Table 7. Substudy B will be single-blind (sponsor unblinded). In Substudy B, up to approximately 630 participants 18 through 64 years of age will be enrolled.

Randomization will be conducted across 3 enrollment cohorts independently due to licensed QIV availability, with enrollment in these cohorts being conducted either concurrently or at different times as required based on operational considerations as shown in Table 2.

Table 2. Substudy B: Enrollment Cohorts

Enrollment Cohort	Total Number of	Number of Participants	Vaccine Group	Vaccine Group Descriptions
Conort	Participants	per Vaccine Group	Number	
1	60	30	1	Licensed QIV (Flucelvax) administered
1	00	30		concurrently in the opposite arm to BNT162b2 (original*/Omi BA.4/BA.5)
			2	Licensed QIV (Flucelvax) administered
				concurrently in the opposite arm to bIRV/bivalent
				BNT162b2 (original/Omi BA.4/BA.5)
2	360	Up to 120	3	qIRV/bivalent BNT162b2 (original/
		-		Omi BA.4/BA.5) at dose-level combination 1 ^a
			4	qIRV/bivalent BNT162b2 (original/
				Omi BA.4/BA.5) at dose-level combination 2 ^a
			5	qIRV/bivalent BNT162b2
				(original/Omi BA.4/BA.5) at dose-level
				combination 3 ^a
3	210	30	6	qIRV/bivalent BNT162b2 (original/
				Omi BA.4/BA.5) at dose-level combination 4 ^a
			7	qIRV/bivalent BNT162b2 (original/
				Omi BA.4/BA.5) at dose-level combination 5 ^a
			8	qIRV/bivalent BNT162b2 (original/
				Omi BA.4/BA.5) at dose-level combination 6 ^a
			9	qIRV/bivalent BNT162b2 (original/
				Omi BA.4/BA.5) at dose-level combination 7 ^a
			10	qIRV/bivalent BNT162b2 (original/
				Omi BA.4/BA.5) at dose-level combination 8 ^a
			11	tIRV/bivalent BNT162b2
				(original/Omi BA.4/BA.5)
			12	qIRV

a. Note: Combinations as shown in Table 7.

Note: * Original refers to the ancestral strain (Wuhan-Hu-1; USA-WA1/2020), also referred to in the protocol as the reference strain.

All participants will be asked to complete a reactogenicity e-diary for 7 days following vaccination.

Blood samples will be collected for immunogenicity assessments prior to vaccination and at 4 weeks after vaccination in Substudy B.

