4. ANALYSIS SETS (POPULATIONS FOR ANALYSIS)

Data for all participants will be assessed to determine if participants meet the criteria for inclusion in each analysis population prior to unblinding and releasing the database and classifications will be documented per standard operating procedures.

Population	Description
Screened	All participants who sign the ICD.
Randomized	All participants who are assigned a randomization number in the IRT system.

Population	Description
Evaluable immunogenicity	All participants who are eligible, receive the study intervention to which they were randomized, have blood drawn for assay testing within the specified time frame after vaccination (26-35 days after vaccination), have at least 1 valid and determinate assay result at the 4-week postvaccination visit, and have no major protocol violations.
mITT immunogenicity	All randomized participants who receive the study intervention and have at least 1 valid and determinate assay result after vaccination.
Safety	All participants who receive the study intervention.

For determination of the evaluable immunogenicity population(s), the last criteria of exclusions due to major protocol violations will be determined via clinical review. The remainder of the criteria will be determined programmatically.

A major protocol violation is a protocol violation that, in the opinion of the sponsor's global medical monitor, would materially affect assessment of immunogenicity, eg, participant receipt of a prohibited vaccine, medication that might affect immune response, or a medication error with suspected decrease in potency of the vaccine. The global medical monitor from the sponsor will identify those participants with a protocol violation prior to any immunogenicity analysis in the study.

For safety, reporting will be as administered and, for immunogenicity, reporting will be as randomized.

For all the immunogenicity endpoints, the analysis will be based on the evaluable immunogenicity population.

An additional analysis may be performed based on the mITT population if there is a large enough difference (>10%) in sample size between the mITT population and the evaluable immunogenicity population.

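### Both SAPs rely on classifying analysis populations before an unblinding that never happens on the sponsor side, so major-violation exclusions can be made knowing the arm and have no dated lock

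*SAP*

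**What the plan says.** **Timing of classification.** Section 4 of the Substudy A SAP and Section 4 of the Substudy B SAP carry the same sentence: data are assessed for "inclusion in each analysis population prior to unblinding and releasing the database".

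**Who is blinded.** For Substudy B, Protocol 10.12.6.2.3 says "sponsor staff will be unblinded to study intervention allocation for the participants enrolled during Substudy B", and Section 2.3 of the Substudy B SAP agrees. For Substudy A, which is open label, Protocol 10.11.6.2.3 says "sponsor staff will be unblinded to study intervention allocation for the participants throughout Substudy A". Protocol 10.11.9.4 adds an exception for Substudy A, "except for staff routinely interacting with sites", which does not agree with 10.11.6.2.3.

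**Who decides.** The evaluable immunogenicity population excludes participants with major protocol violations. In the Substudy B SAP a violation is major if, "in the opinion of the sponsor's global medical monitor, would materially affect assessment of immunogenicity"; the remaining criteria are programmed. The Substudy A SAP likewise leaves it to the opinion of the sponsor's medical monitor.

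**When the monitor decides.** The Substudy A SAP requires deviations to be identified before any analysis. The Substudy B SAP requires it before any immunogenicity analysis in the study.

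**Later looks.** The Substudy A SAP also says: "For each reporting event, the most current endorsed version of the PIPD list must be used". Its Section 7.2 provides for unblinded sponsor reviews while the study runs. For Substudy B, Protocol 10.12.9.5 says "Analyses (immunogenicity or safety) may be performed at any time", and Section 7.1.1 of the Substudy B SAP repeats this.

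**The concern.** A rule that populations are settled before unblinding is meant to ensure that whoever decides on exclusions does not know which arm a participant is in. Here no such moment exists for the sponsor, and no text masks the medical monitor to arm or titers. By contrast, Protocol 8.2.1 does mask the laboratory analysts. The measurement is protected; the decision on whose measurement counts is not.

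The secondary immunogenicity results rest on the evaluable population. The Substudy B SAP (6.2.1.2) also compares groups with Groups 1 and 12, each of about 30 participants, where a few uneven exclusions weigh most. Protocol 10.1.5.1 lists immunogenicity among the data the internal review committee sees. At stake is whether a reader can be sure that exclusions did not depend on arm.

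**Working it through.** This is mainly a check of passages against each other. The plan gives no figure to reproduce, and neither substudy has a hypothesis, margin or power statement.

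**Step 1: is there an unblinding event?** Not in Substudy A, where participants, sites and sponsor staff all know the allocation. In Substudy B only participants are blinded. The exception in Protocol 10.11.9.4 does not help: it conflicts with 10.11.6.2.3, and nothing places the medical monitor in the excepted group. The wording therefore supplies no masking. The other half of the clause, release of the database, remains a real milestone.

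**Step 2: is the rule to classify before analysis operable?**

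- *Substudy A.* The SAP plans serology at weeks 1, 4 and 8 (6.2.1.1). Four-week safety and immunogenicity data go to the internal review committee (Protocol 10.11.4.1). Nonstudy coronavirus and influenza vaccines are prohibited through Visit 5, at 8 weeks (Protocol 10.11.6.7.1). A disqualifying deviation can thus arise after 4-week data have been reviewed, and the latest list is used at each reporting event. The SAP does not say how this fits with identifying deviations before any analysis.
- *Substudy B.* Three cohorts may enroll at different times (SAP 2.3), and Groups 1, 3, 4 and 5 enrolled under a prior protocol version (Protocol 1.2). If an early cohort is analyzed first, violations in participants not yet enrolled cannot have been identified before that analysis. No lock per cohort or per participant is written.

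**Step 3: how much judgement is there?** In the SAP definitions, the major-violation call is the judgement-based criterion. Protocol 10.12.9.2 also lets Substudy B participants with influenza or COVID-19 onset be removed at discretion; the Substudy B SAP does not define this.

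**Step 4: size, as a worst case.** Assume that the >10% mITT trigger applies per group, that every exclusion is a judgement call, and that all fall on one response category. In a group of 30, the most exclusions that do not exceed the trigger are 0.10 × 30 = 3. For an assumed 18/30 = 60.0%:

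- drop 3 non-responders: 18/27 = 66.7%, a shift of +6.7 points;
- drop 3 responders: (18 − 3)/27 = 15/27 = 55.6%, a shift of −4.4 points;
- exact (Clopper-Pearson) 95% CI for 18/30: 40.6% to 77.3%, which contains both.

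Other assumed rates at n = 30:

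| Assumed | Drop 3 non-responders | Drop 3 responders | Exact 95% CI |
|---|---|---|---|
| 9/30 = 30.0% | 9/27 = 33.3% | 6/27 = 22.2% | 14.7% to 49.4% |
| 15/30 = 50.0% | 15/27 = 55.6% | 12/27 = 44.4% | 31.3% to 68.7% |
| 21/30 = 70.0% | 21/27 = 77.8% | 18/27 = 66.7% | 50.6% to 85.3% |

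For titers, simulated normal log10 values with the 3 lowest of 30 dropped raise the GMT by a factor of about 1.19, 1.24 or 1.29 for an assumed log10 SD of 0.4, 0.5 or 0.6.

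**The case against.** The strongest reply is that the plan has real protections, and most of it stands.

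- Both SAPs tell the monitor to identify violations before analysis, so using known titers to decide would breach the written plan.
- Classifications are documented under standard procedures. Exclusions from each population are tabulated by group with reasons (Substudy A SAP 6.5.2.1, Substudy B SAP 6.4.3.1), so lopsided exclusion would be visible.
- The Substudy A SAP (6.2.1.2) allows an mITT summary without any size condition.
- The sentence on the latest deviation list can be read as version control. A nonstudy vaccine given in week 5 is a new fact, not a second opinion on an old one.
- The trigger counts every reason for leaving the evaluable set, including out-of-window draws and missing 4-week results, so judgement would seldom account for all 3 exclusions.
- Immunogenicity is secondary and descriptive, and Protocol 10.12.4.1 bases the choice of Substudy B groups for further study on safety data.

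A reader might go further and infer that in both substudies evaluability can be reopened at each reporting event by someone who has already seen the titers. The documents do not support that. The deviation-list sentence is in the Substudy A SAP only, and neither SAP provides for reversing a settled classification. Substudy B has a single postvaccination draw, at 4 weeks, so no participant there has an earlier postvaccination titer.

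None of this supplies the missing masking or a dated lock.

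**Conclusion.** The concern holds in a limited form. The blinding safeguard stated in both SAPs does not exist, and the major-violation exclusion can be made knowing the arm. The requirement to classify before analysis is sound in intent. In Substudy A it is not reconciled with a list refreshed at each reporting event; in Substudy B it lacks a lock per cohort.

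The possible effect is modest. Under the worst-case assumptions, a 60% response moves by +6.7 or −4.4 points in a group of 30, well within sampling error. It would be wrong to add the two into an 11-point spread, since they are opposite extremes that cannot both occur. The documents give no deviation rate, so the likely bias cannot be estimated. Because the analyses are descriptive and the remedy is cheap, this should be corrected, but it does not undermine the substudies.

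**What to change.** In Section 4 of both SAPs:

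1. Replace the reference to unblinding with a dated lock of the major-violation list, made before the first immunogenicity analysis that includes the participant: per cohort in Substudy B, per reporting event in Substudy A.
2. Have the medical monitor work from listings without study intervention or assay results.
3. Handle deviations that need product information, such as a wrong vaccine or a potency-related medication error, by a prespecified rule or by a reviewer without access to titers.
4. Add deviations that occur or come to light after the lock with date and reason, and also show results under the earlier classification.
5. In the Substudy A SAP, reconcile the deviation-list sentence with the requirement to identify deviations before any analysis.
6. If the discretionary removal in Protocol 10.12.9.2 is used in Substudy B, define it and put it under the same lock.

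The cost is SAP wording, a masked listing and slightly more reporting. No new data are needed, and nothing changes for participants.

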5. GENERAL METHODOLOGY AND CONVENTIONS

5.1. Hypotheses and Decision Rules

There are no hypotheses and decision rules defined for the study. A descriptive estimation approach will be used to assess all study objectives in the study. Point estimates and nominal 95% CIs will be provided for all safety and immunogenicity endpoints at each planned analysis. No formal multiplicity adjustments will be applied due to multiple endpoints or multiple evaluations for the same endpoint.

5.2. General Methods

CIs for all endpoints in the statistical analysis will be presented as 2-sided at the 95% level unless specified otherwise.

5.2.1. Analyses for Binary Endpoints

Descriptive statistics for binary variables (eg, proportions) are the percentage (%), the numerator (n) and the denominator (N) used in the percentage calculation, and the 95% CIs where applicable. The exact 95% CI for binary endpoints for each group will be computed using the Clopper-Pearson method.¹

For the between-group difference, the 2-sided 95% CI will be calculated using the Miettinen and Nurminen method.

5.2.2. Analyses for Continuous Endpoints

5.2.2.1. Geometric Mean Titers

The GMTs will be calculated as the mean of the assay results after making the logarithm transformation and then exponentiating the mean to express results on the original scale. Two-sided 95% CIs will be obtained by taking log transforms of assay results, calculating the 95% CI with reference to the Student t distribution, and then exponentiating the confidence limits.

5.2.2.2. Geometric Mean Ratio

Unadjusted GMR

The GMR will be calculated as the difference in the means of logarithmically transformed assay results between 2 vaccine groups and exponentiating the difference. The 2-sided 95% CI will be obtained by exponentiating the limits of the CI for the mean difference of the logarithmically transformed assay results based on the Student t distribution.

Model-Based GMR

A linear regression model, including the log baseline titer as a covariate, will be used to analyze the titers after log transformation. The GMR and the 2-sided 95% CI will be calculated by exponentiating the difference in LS means and corresponding CI estimated from the regression model.

5.2.2.3. Geometric Mean Fold Rises

The GMFR for each vaccine group is defined as the geometric mean of the fold rises in the assay results from the specified time points. Only data from participants with nonmissing assay results at both time points will be included in the GMFR calculation.

GMFRs will be calculated as the mean of the difference of logarithmically transformed assay results (later time point minus earlier time point) and exponentiating the mean. The associated 2-sided 95% CIs will be obtained by constructing CIs using the Student t distribution for the mean difference on the logarithm scale and exponentiating the confidence limits.

5.2.2.4. Reverse Cumulative Distribution Curves

Empirical RCDCs will plot proportions of participants with values equal to or exceeding a specified assay value versus the indicated assay value, for all observed assay values. Data points will be joined by a step function with the line first going down and then to the right to the next assay value.

5.3. Methods to Manage Missing Data

Standard algorithms on handling missing AE dates will be applied according to Pfizer safety rules. A completely missing start date for an AE is not allowed in data collection. For derived variables based on reactogenicity data, if any day of the 7-day e-diary is available, the "any day (Day 1 through Day 7)" data will be considered nonmissing. It is expected that these reactogenicity events would be queried by the investigator for the missing e-diary days and would be entered in the AE CRF if any reactogenicity was not reported in the e-diary due to missed days. Therefore, the primary analysis will use the reactogenicity recorded in the AE CRF to impute the partially missing e-diary data to estimate the reactogenicity rate during the e-diary collection period. The AE CRF is designed as a log page, which means only events that occurred will be recorded and events that did not occur will not be recorded. Therefore, all remaining missing days are considered as having answered "no." This imputation can reasonably estimate the reactogenicity event rates during the e-diary collection period.

Antibody titers below the LLOQ, denoted as BLQ, or below the LOD will be set to $0.5 \times \text{LLOQ}$ for GMT analysis. No other missing assay data will be imputed in the analyses.

When calculating a fold rise, the assay results will be converted to $0.5 \times LLOQ$ if assay results are < LLOQ, except when the prevaccination assay result is < LLOQ while the postvaccination result is $\ge LLOQ$, in which case the prevaccination value will be set to LLOQ. If both the numerator and denominator are < LLOQ, then both will be converted in the same way.

Values for sera that are insufficient, indeterminate results, or values recorded as "not done" will be set to "missing."

LLOQs for each assay used in this study will be included in serology data transfer once they are available.

6. ANALYSES AND SUMMARIES

6.1. Primary Endpoints

6.1.1. Local Reactions and Systemic Events

6.1.1.1. Main Analysis

• Estimand: The proportion of participants reporting local reactions and systemic events within 7 days after vaccination (Section 2.2).

- Analysis set: Safety population (Section 4) for participants with any e-diary data through 7 days.
- Analysis time point: Within 7 days after vaccination (Section 3.1).
- Analysis methodology: 95% CI of the proportion of participants reporting each reaction or event using the Clopper-Pearson method (Section 5.2.1).
- Intercurrent events and missing data: Missing values will not be imputed.
- Reporting results: Descriptive statistics including counts, point estimates, and the associated exact 2-sided 95% CIs using the Clopper-Pearson method for the proportion of participants 18 through 64 years of age reporting each (and any) reaction or event for each vaccine group. The denominator used in the proportion calculation will be the number of participants with any reactogenicity data reported after vaccination.

6.1.1.2. Sensitivity/Supplementary Analyses

To support the assessment of reactogenicity, the endpoints will be summarized with the same analysis time points and analysis population:

- Duration (days) of each local reaction and each systemic event after vaccination.
- Onset day of each local reaction and each systemic event after vaccination.
- Presence of each local reaction and each systemic event, for "any day (Day 1 through Day 7)." Any severe local reactions or any severe systemic events for "any day (Day 1 through Day 7)."
- The proportion of participants reporting local reactions and systemic events within 7 days after vaccination based only on e-diary data. These continuous endpoints will be summarized by displaying the n, mean, median, standard deviation, minimum, and maximum for each study intervention group for participants 18 through 64 years of age.

Summaries of the proportion of participants with each local reaction and systemic event occurring within 7 days of vaccination (by maximum severity) will also be created using bar charts.

